4 STUDY DESIGN AND PROCEDURES

4.1 EXPERIMENTAL STUDY DESIGN

A multicenter, prospective, controlled, randomized (moderate hypothermia during 24 hours \pm 1h versus normothermia), comparative open trial will be conducted on two parallel groups of patients with CS treated with VA-ECMO.

4.1.1 Common management for all patients before and during intervention

For all patient enrolled in the study, VA-ECMO will be initiated in accordance to the local practice with flow settings to ensure sufficient tissue perfusion.

With the exception of temperature control, all other diagnostic, therapeutic and weaning procedures will be done according to the current standard of care at the tertiary CV center and at the discretion of the investigator.

For reference, the current standard of care is described in appendix A

4.1.2 Heater-Cooler Unit and temperature control for all patients

Each circuit will be associated with a device able to control temperature used in this study in conformity of the device CE Label such as "Heater-Cooler Unit HCU 35 from Maquet compagny".

These devices are available in each center. This device allows a perfect control and hold of the target temperature. The water tank for the patient circuits is divided into two parts to ensure quick temperature adjustments at the outlets. In addition, it has exceptional cooling capacity through its fast

ice-building technique using highly effective cooling plates and a powerful compressor. In our study each center will use his local heater-cooler unit to control temperature (described in Appendix B).

Temperature management (hypothermia, normothermia or reheating) will be performed using the heat controller of the VA-ECMO circuit and other classical temperature management if necessary (external or internal technique).

4.1.3 **Temperature assessment method**

During therapeutic hypothermia, all centers monitore central temperature. Central temperature will be measured in each group in accordance with local practice (e.g bladder catheter, oesophageal probe...)

In both group, temperature will be measured every two hours during intervention (time during the first 92 hours at the allocated group (cf figure in chapter 4.1).

4.1.4 Inclusion and randomization of patient

The inclusion and randomization of the patient will be performed after VA-ECMO indication and implementation. Inclusion and study intervention will be performed as soon as possible **during the first 6 hours (preferably 4 hours) after VA-ECMO initiation.**

After eligibility verification, complete clinical examination and inform consent process (cf chapter 13.2), patient will be randomized. The patients will be placed on moderate hypothermia ($33^{\circ}C \le T^{\circ}C \le 34^{\circ}C$) or maintained on normothermia $36^{\circ}C \le T^{\circ}C \le 37^{\circ}C$ during 24 hours ± 1h according to the group.

Data collected (nonspecific to the study) at inclusion and during ICU stay after randomization : demographic data, medical history, SOFA score, biological data (Arterial Lactate, ASAT, ALAT, urea, creatinine, coagulation parameters..), amount of paralyzing agent and sedative, amount of insulin...), concomitant drugs, treatments (fluid amount, vasopressors, inotropes, echocardiography at inclusion performed before study intervention (echocardiography data result from usual care...))...

4.1.5 Moderate hypothermia group

Moderate hypothermia will be induced as soon as possible **during the first 6 hours (preferably 4 hours) after VA-ECMO initiation (H0) and randomization.** Moderate hypothermia will be induced using the heat controller of the VA-ECMO circuit and other classical temperature management if necessary (external or internal technique). Temperature will be maintained between $33^{\circ}C \le T^{\circ}C \le 34^{\circ}C$ during 24 hours ± 1h followed by a progressive reheating (0.2±0.1°C/hour) to reach 37°C. Température at $37^{\circ}C \pm 0.3^{\circ}C$ will be maintained during 48 hours ± 4h after having reached 37 °C.

The potential physiological effects of hypothermia and their managements based on literature are described in chapter 1.4.2. Their managements will be done according to the local practice and to the discretion of investigator.

4.1.6 Normothermia group

The extracorporeal life support organization (ELSO) recommends "Temperature can be maintained at any level by adjusting the temperature of the water bath. Temperature is usually maintained close to 37° C." A large amount of patients that need VA-ECMO experiment a cardiac arrest before ECMO implantation. Concerning the patients with cardiac arrest it is now recommended to maintain the patients between 33 and 36 degrees. Therefore,the temperature will be maintained at Therefore the temperature will be maintained at $36^{\circ}C \le T^{\circ}C \le 37^{\circ}C$ under VA-ECMO.

4.1.7 Discontinuation of experimental study intervention (moderate hypothermia group)

In the moderate hyperthermia group, in cases of uncontrolled bleeding (bleeding despite medical intervention (surgery or drugs)), moderate hypothermia will be stopped and resumed as soon as the bleeding is controlled for a total duration of 24 hours \pm 1h of moderate hypothermia. Under VA-ECMO, rhythms disturbances are not an indication to stop moderate hypothermia.

4.1.8 **Prohibited treatment for the subject participation**

None, all medications or treatments are authorized.

4.1.9 Follow up after intervention (H48, day 7, day 30 (± 5 days), day 60 (± 5 days), Day 180 (± 15 days) (end of the study) after randomization for all patient)

Vital status (and date/cause of death) will be collected for all patients and if necessary obtained by the investigator or his staff by contacting the patient, the family or his/her primary care physician.

4.2 FLOWCHART

			After randomization					
	Inclusion		H0	H48	Day 7	Day 30 ± 5 days	Day 60 ± 5 days	Day 180 (6 months) (± 15 days)
Informed and signature of consent (cf chap 13.2)	х	n (a)						
Inclusion and non-inclusion criteria verification	x	Randomization						
Study Intervention Moderate hypothermia/normothermia (b)		nobri	х					
Vital Status (date and cause of death)		Râ		x	х	х	х	х
Medical events reporting (AE/SAE)	x		x	x	х	X (LT or fatal)	X (LT or fatal)	X (LT or fatal)

- a) During the first 6 hours (preferably 4 hours) after VA-ECMO implementation
- b) Induced as soon as possible during the first 6 hours (preferably 4 hours) after VA-ECMO implementation and randomization

LT : life threatening

4.3 BIAS CONSIDERATION

4.3.1 Randomization procedure

Randomization will be performed after enrolment using a centralized on-line randomization system (Cleanweb[™]) available 24h/24h.

Treatments arms :

- **Experimental group:** Patients with CS allocated to a strategy of moderate hypothermia (33°C≤ T°C ≤34°C) associated with usual care.
- Control group: Patients with CS allocated to a strategy of normothermia 36°C≤ T°C ≤37°C associated with usual care.

Randomization will be stratified on the center. The randomization plan will be devised by Centre investigation Clinique 1433 module Plurithématique de Nancy, France.

4.3.2 **Replacement procedures for patients**

All patients non randomized will be replaced to reach 334 patients (167 patients in each group) (cf chapter 11.8)

4.4 STUDY PERIOD

Duration of participation of each patient: **6 months (D180)** Anticipated duration of recruitment: **36 months** Anticipated total duration of the study (statistical analysis included): **49 months**

4.5 TERMINATION RULES

4.5.1 **Patient Premature termination**

Any subject can stop his participation to the research at any time and for any reason.

The investigator can permanently end a subject's participation in the research for any reason that affects the subject's safety or which would be in the subject's best interests.

If a subject leaves the research prematurely, data relating to the subject can be used unless an objection was recorded when the subject signed the consent form.

4.5.2 Exclusion period

Patient cannot participate simultaneously in other biomedical research during the research. There is no exclusion period.

4.5.3 Follow-up after end of study

Patient will be follow up in accordance with the current standard of care.

4.6 DATA LIST NOT AVAILABLE IN THE PATIENT FILE

All medical data will be available in the patient medical file.

5 STUDY POPULATION

5.1 PARTICIPATING CENTERS

Patients will be enrolled in 17 ECMO French centers. All centers are well trained for VA-ECMO.

5.2 PATIENT SCREENING AND ENROLMENT

All intubated patients with CS supported with VA-ECMO will be screened. Patients with CS treated with VA-ECMO in the intensive care unit meeting all of the inclusion and noninclusion criteria will be enrolled in the study (emergency consent process cf chapiter 13.2). Reasons for non-eligibility will be listed in a dedicated screening log file.

5.3 INCLUSION CRITERIA

- Age ≥ 18 years
- Intubated patients with cardiogenic shock treated with VA-ECMO
- Patient affiliated to social security plan

5.4 NON-INCLUSION CRITERIA

- VA-ECMO after cardiac surgery for heart transplantation or heart lung transplantation or left or biventricular assist device implantation
- VA-ECMO for acute poisoning with cardio-toxic drugs
- Pregnancy
- Uncontrolled bleeding (bleeding despite medical intervention (surgery or drugs))
- Implantation of VA-ECMO under cardiac massage with a duration of cardiac massage ≥ 45 minutes
- Out of hospital refractory cardiac arrest
- Cerebral deficit with fixed dilated pupils
- Participation in another interventional research involving therapeutic modifications
- Patient moribund on the day of randomization
- Irreversible neurological pathology
- Minor patients
- Patients under tutelage

6 METHODS USED FOR THE EVALUATION OF EFFICACY

Cf chapter 3

7 SAFETY ASSESSMENT

7.1 DESCRIPTION OF SAFETY ASSESSMENT PARAMETERS, METHOD AND CALENDAR USED FOR THE EVALUATION OF SAFETY

In both group, the VA-ECMO implementation and monitoring will be done in accordance with the current standard of care. All adverse events will be documented during this study from medical examinations, biological and imaging exams if necessary and will be complied in the electronic case report form (eCRF).

In particular, glycaemia, blood gas and coagulation will be followed up and the occurrence of shivering, modifications in blood gas management, hyperglycemia, electrocardiographic changes, mild coagulopathy and increased sensitivity to infection will all be recorded as adverse events.

Uncontrolled bleeding and coagulation disorders that require blood cells or platelet transfusion will be considered as serious events.

In normothermia group, no additional risk linked to research is expected.

All adverse events between inclusion and D7 will be recorded.

After D7, only serious life-threatening and fatal adverse events will be recorded until the end of the follow-up of the patient.

7.2 REPORTING AND TRANSMISSIONS OF SAE/R

7.2.1 **Definitions:**

Adverse event (AE) (article R.1123-39 of the French Public Health Code): Any harmful event occurring in a person participating in a biomedical study, whether or not this event is in relation or not with the study or the product studied.

Serious adverse event (SAE) (article R.1123-39 of the French Public Health Code and ICH E2B guide). Any adverse event that:

- ✓ results in death,
- ✓ is life-threatening,
- ✓ requires hospitalization or prolongation of existing hospitalization,
- ✓ results in persistent or significant incapacity/disability,
- ✓ or any other medically important condition,
- \checkmark and when regarding a medicinal product, whatever the administered dose.

The expression "life-threatening" is reserved to immediate threat to life occurring at the time of adverse event occurrence, and this, independently of the consequences that corrective or palliative treatments may have.

Certain circumstances that require hospitalization do not correspond to the "hospitalization" seriousness criterion, such as:

- admission for administrative or social reason,
- hospitalization predefined by the protocol,
- hospitalization for medical treatment or surgery that was scheduled before the start of study,
- out-patient hospitalization.

Unexpected serious adverse effect (article R.1123-39 of the French Public Health Code):

Any adverse effect, of which the nature, the severity or the progression does not concord with the information in the submissions to the ethics committee (Comité de Protection des Personnes, CPP) and the competent authority.

New safety data, that may lead to the re-evaluation of the benefit-risk ratio and the risks associated with the study, or that may be sufficient to consider modifications to the study documents, study conduct, and, if applicable, the use of the product.

7.2.2 List of expected adverse events suspected

All potential adverse events associated with the use of hypothermia may be also encountered in the control group (normothermia group) and are well described during an ICU stay for cardiogenic shock (cf chapter 1.4.2).

- Shivering
- Modifications in blood gas management
- Hyperglycemia
- Electrocardiographic changes
- Mild coagulopathy
- Increased sensitivity to infection

Therefore, we will record in the patient's e-CRF the occurrence of hyperglycemia (appreciated by the amount of insulin), nosocomial infection and hemorrhagic disorder (number of packed red cell transfused).

We will consider as **serious adverse events** in the hypothermia group the occurrence of uncontrolled bleeding. In this case, hypothermia will be stopped and resumed as soon as the bleeding is controlled for a total duration of 24 hours.

7.2.3 Serious adverse events/ reactions and new facts reporting

- As soon as an investigator becomes aware of a SAE/R or a new fact, he/she advises the sponsor without delay by faxing the SAE/R declaration form at **[name]**.
- If it is a an *unexpected serious adverse reactions* (USAR) or if it is a new fact, the sponsor will contact the investigator in order to prepare an initial report which will be forwarded to the ANSM, the CPP and to the coordinating investigator within 7 days in case of death or life threatening SAE, otherwise within 15 days. An additional information will be forwarded within 7 days of death or life-threatening SAE.
- When the event is not resolved at the time of fax transmission, the investigator must send a supplementary report to document the changes or to update the missing data.
- If it is an *expected serious adverse effect*, the sponsor will compile it for the drafting of annual safety reports.
- *Expected non-serious adverse reactions* will be briefly described by the investigator on the summary sheet dedicated to this effect in the data collection notebook.

7.2.4 Non-serious adverse events/ reactions reporting

Non serious adverse event/reaction will be compiled in the eCRF. These data will be available to sponsor for any safety evaluation for the study and for the final report. Date of event and his resolution will be described in the eCRF.

7.2.5 Adverse event/reaction monitoring

Any patient presenting an adverse event must be followed until resolution or stabilization thereof :

- If the event is not serious, evolution/changes will be noted on the relevant page of the case report form in the designated section reserved for this purpose.
- If the event is serious, a SAE/R follow-up will be sent to the sponsor.

7.2.6 Safety report

- Annual safety reports: the sponsor words the annual safety reports and submits them to the ANSM, the CPP and the coordinating investigator. The coordinating investigator will transmit all data necessary for the preparation of this report to the sponsor.

- Final report: the final report is prepared after data reconciliation with the safety data by the sponsor and the coordinating investigator within one year of the end of the study. All investigators are informed of the results of the study. A summary is forwarded to the French competent authorities (ANSM) by the sponsor.

8.1.2 Data safety monitoring board (DSMB)

The DSMB will be responsible for the review of the study data in order to identify any potential safety issues. Based on the safety data, the DSMB may recommend modifications to the protocol (e.g. amendments, termination of the study) and, when needed, the DSMB will decide on stoppage rules. Members of this board are independent of the study. The DSMB will be composed of two intensivists and a biostatistician or methodologist.

The chairman of the DSMB will inform the Steering Committee members in writing whether or not any safety issues are identified during DSMB meetings or telephone conferences.

The DSMB will review aggregate SAEs at 6 months intervals. At this time, the DSMB will recommend to the HYPO-ECMO steering committee and sponsor to a) continue the study as scheduled, b) suspend enrolment, or c) obtain more information before a recommendation can be made.

9 FEASIBILITY

Considering the main objective, the HYPO-ECMO trial will be a pragmatic study in order to facilitate patient inclusion and monitoring.

HYPO ECMO project is included in the large clinical network F-CRIN (French Clinical Research Infrastructure Network) INI CRCT (Cardiovascular and Renal Clinical Trialists coordinated by [name] www.inicrct.org<http://www.inicrct.org/>).

10 DATA MANAGEMENT AND STATISTICS

10.1 DATA MANAGEMENT

10.1.1 Electronic Case report form

Data management will be carried out by the "Centre d'Investigation Clinique 1433, Plurithématique department, CHRU-Nancy". Data collection for this study will be made via an electronic Case Report Form (eCRF).

Each patient will be identified on the eCRF with his/her initials (first letter of the name and first letter of the surname), birth date (month and year) and an identification number indicating his/her rank of inclusion into the study. Investigators must not provide other personal information about the patients to the staff in charge of the data management and data analysis (i.e full names and last known addresses).

The investigator or a qualified designee from the site should complete the eCRF as soon as the data are available. The data manager in charge of the study will provide access codes as well as guidance for the completion of e-CRF.

As a matter of regulations, the investigator is responsible for the accuracy and authenticity of all clinical data entered onto eCRFs. Each page of the completed eCRFs must be reviewed for accuracy by the investigator, corrected as necessary, and e-signed.

The investigator's e-signature serves to attest that the investigator has reviewed the information contained on the eCRF and is true and accurate.

11 DATA ANALYSIS AND STATISTICAL DETERMINATION

11.1 DESCRIPTION OF ANTICIPATED STATISTICAL ANALYSIS METHODS

11.1.1 Statistical analysis for the primary endpoint

The differences between the 2 study groups (i.e. intervention and controls) in the risk of all-cause mortality at day 30 following randomization will be studied using the Chi-2 test. To illustrate the association, both an odd-ratio and a hazard ratio will be provided. In addition, survival curves using the Kaplan-Meier method will be constructed.

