3.3 STUDY OUCOME MEASURES

3.3.1 **Primary endpoints**

All-cause mortality at day 30 following randomization (i.e. 30 day mortality)

3.3.2 **Secondary endpoints:**

[figure not shown]
- All-cause mortality at 48 hours and day 7, 60, 180
- VA-ECMO duration
- Composite endpoint of death, cardiac transplant, escalation to LVAD, stroke at days 30, 60, 180
- Cumulated amount of administered fluids and duration of vasopressors use in ICU
- Duration to normalization of lactate
- Number of days alive without organ failure(s), defined with the SOFA score and its components (respiratory, liver, coagulation and renal), between inclusion, D7 and D30
- Duration of mechanical ventilation and the number of days between inclusion and day 30/ day 60/ day 180, alive without mechanical ventilation
- Number of days alive without renal replacement therapy, and the number of days, between inclusion and day 30, day 60 and day 180, without renal replacement therapy

- Duration of ICU stay, of hospitalization
- Number of severe and moderate bleeding complications (GUSTO-definition, N Engl J Med. 1993;329:673–682) and the number of packed red blood cells transfused under VA-ECMO
- Infection probability: pulmonary, blood and VA-ECMO cannulaes

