11.1.2 Statistical analysis for the secondary endpoints

For the secondary analysis of a) all-cause mortality at 48 hours and day 7, 60, 180, b) the composite endpoint of death, cardiac transplant, escalation to LVAD, stroke at days 30, 60, 180 the same analysis strategy will be performed as for the primary endpoint.

Unpaired t-test will be performed, after checking for normality of the variable's distribution, for the outcomes mentioned below. Importantly, In case of non-normal distributions (which is highly likely for all duration data), non-parametric tests will be performed.

- VA-ECMO duration
- cumulated amount of administered fluids and duration of vasopressors use
- duration to normalization of lactate
- Number of days alive without organ failure(s), defined with the SOFA score and its components (respiratory, liver, coagulation and renal), between inclusion, D7 and D30
- duration of mechanical ventilation and the number of days, between inclusion and day 30/ day 60/ day 180, alive without a mechanical ventilation
- number of days alive without renal replacement therapy, and the number of days, between inclusion and day 30/ day 60/ day 180, without renal replacement therapy
- duration of ICU stay, of hospitalization
- number of severe and moderate bleeding complications (gusto-definition) and number of packed red blood cells transfused under VA-ECMO

Chi-square tests (or Fisher exact test in case of insufficient number of expected patients in on of the 2x2 cell) will be performed for the outcomes mentioned below:

- Pulmonary, blood and VA-ECMO cannulaes infections

To illustrate the association, an odd-ratio will be provided.

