11.2 SAMPLE SIZE CONSIDERATION

We considered that mortality in cardiogenic patients supported with VA-ECMO will be 50% (based both on ELSO data, [name] data (*Crit Care Med.* 2008 May;36(5):1404-11) and study principal investigator's personal data (database of 150 patients)

The objective of the study is to demonstrate the superiority of the treatment with VA-ECMO plus moderate hypothermia as compared to VA-ECMO alone on mortality.

Therefore, considering a total event risk (for the primary endpoint) of 50 % in the control group, a sample size of N = 167 patients/group will detecting a 15% absolute difference in favor the VA-ECMO group using a chi-square test with a 80 % power and considering a two-sided global alpha level of 5% using the LanDe Mets method with O'BrienFleming boundary for one interim analysis (efficacy and futility) after inclusion of 2/3 of the patients.

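### The primary day-30 mortality test is a valid but unadjusted chi-square; prespecified adjustment for age, SOFA and arterial lactate could gain power at the same 334 patients

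*Protocol*

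**What the plan says.** - **Primary test.** Section 11.1.1 compares the groups "in the risk of all-cause mortality at day 30 following randomization will be studied using the Chi-2 test". It adds: "To illustrate the association, both an odd-ratio and a hazard ratio will be provided", together with Kaplan-Meier curves. No covariate is named. The synopsis repeats the chi-square.
- **Sample size.** Section 11.2 rests on the same test and takes the control-arm risk to be 50%. On that basis it states that "a sample size of N = 167 patients/group will detecting a 15% absolute difference", with 80% power and a two-sided overall level of 5%. Section 11.3 sets 4.9% for the final analysis.
- **Other endpoints.** For mortality at 48 hours and days 7, 60 and 180, and for the composite at days 30, 60 and 180, section 11.1.2 says "the same analysis strategy will be performed as for the primary endpoint".
- **Baseline data.** Section 4.1.4 lists "demographic data, medical history, SOFA score, biological data (Arterial Lactate, ASAT, ALAT, urea, creatinine, coagulation parameters" among routine-care data collected at inclusion and during the ICU stay. Age is not named there. It falls under demographic data and can be derived from the birth month and year on the eCRF (section 10.1.1).
- **Randomisation.** Section 4.3.1 stratifies on centre only. No severity measure is a stratification factor.

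The protocol contains no covariate-adjusted analysis, either primary or as a sensitivity analysis.

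**The concern.** Severity is balanced between arms by chance alone, and the planned test uses none of the severity data. If those data predict day-30 death, a prespecified adjusted analysis answers the same question more precisely with the same patients.

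The trial has little power to spare. It has about 80% power for a 15-point absolute reduction, which section 1.4.1 itself calls large. With the unpooled formula used below and the same control risk of 50%, power at 167 per arm is 60.1% for a 12-point effect and 45.1% for a 10-point effect. A cheap gain in precision is worth having.

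There is also a question of timing. If the arms differ visibly in SOFA or lactate, an adjustment chosen after seeing that difference would be post hoc.

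**Working it through.** **Inputs from the protocol.** Control risk 50% and a 15-point difference, hence 35%; 167 per arm; 80% power; two-sided 5% overall (section 11.2). Final level 4.9% (section 11.3).

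**Input assumed.** How well age, SOFA and lactate together predict day-30 death. The protocol gives no figure.

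**Step 1: the plan's own figure.** With unpooled variance, n per arm = (1.960 + 0.842)² × (0.50×0.50 + 0.35×0.65) / 0.15² = 166.6, so 167. This reproduces. The pooled-variance formula gives 170.

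**Step 2: power of the planned test.** SE = √(0.4775/167) = 0.0535. At the 4.9% level the critical value is 1.969, so power = Φ(0.15/0.0535 − 1.969) = Φ(0.837) = 79.9%. Summing exact binomial probabilities for the chi-square gives 80.1%. The stated 80% is delivered.

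**Step 3: power with adjustment.** Two simulations used 167 per arm, 4,000 trials per setting, the 4.9% level and marginal risks of 50% and 35%. A used three equally weighted covariates and the logistic Wald test for arm. B used one severity score and the standardised risk difference.

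| Assumed AUC | A: chi-square → adjusted | B: chi-square → adjusted | Gain (points) |
|---|---|---|---|
| 0.63 (A), 0.65 (B) | 78.6 → 80.0% | 79.7 → 81.6% | 1 to 2 |
| 0.69 | 79.9 → 82.9% | 80.5 → 83.5% | 3 to 4 |
| 0.74 | 79.8 → 85.5% | 80.3 → 85.4% | 5 to 6 |
| 0.78 | 79.5 → 88.0% | 81.5 → 89.7% | 8 to 9 |

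- A repeat of the single-score simulation gave adjusted power of 81.6, 83.4, 86.3 and 89.7% in the four rows.
- With covariates of no prognostic value, power went from 80.3 to 79.3% with the Wald test and from 79.5 to 79.2% in the repeat.
- Under no treatment effect the adjusted tests rejected in 4.1 to 5.8% of trials across all runs. The chi-square rejected in 4.9 to 5.9% in simulation A.

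The shortcut that multiplies the variance by (1 − R²) is somewhat optimistic. At AUC 0.74, where R² = 0.176 in simulation A, it gives Φ(0.15/(0.0535×√0.824) − 1.969) = 86.9%, against about 85.5% simulated. The gains above are therefore taken from simulation. The simulations contain no centre effect.

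**Step 4: size of chance imbalance.** One standard error of the difference in a standardised score is √(2/167) = 0.109 SD. The shift in the unadjusted risk difference is √R² × √(0.425×0.575) × 0.109. For R² from 0.055 to 0.234 (AUC 0.63 to 0.78 in simulation A) this is 1.3 to 2.6 points, and twice that (2.5 to 5.2 points) for a two-standard-error imbalance. The chi-square's standard error already allows for this variation. Adjustment removes much of it.

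**The case against.** The strongest case on the other side is that nothing here is wrong. Endpoint, test and sample size agree with each other, 167 reproduces, and the power is as stated. That stands in full.

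A reader might infer that leaving chance severity imbalance uncorrected biases the result. It does not: the test's error rate already covers such imbalance over repeated randomisation. What is lost is precision, and accuracy of the estimate given the imbalance actually seen.

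A reader might also expect a large gain as a matter of course. The protocol gives no basis for one. All patients are intubated and on VA-ECMO, the worst prognoses are excluded (section 5.4), and inclusion follows VA-ECMO implementation, so baseline values may already reflect support. Weak covariates are possible, and then the gain is 1 to 2 points or nothing.

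Nor does section 4.1.4 show that pre-intervention values exist for every patient. Only echocardiography is expressly placed before the intervention, and the flowchart has no row for SOFA or lactate. Completeness and timing are assumptions.

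It is tempting to extend the point to "duration to normalization of lactate", on the view that baseline lactate largely determines it. The protocol neither says nor quantifies this, so that endpoint is not part of the point.

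Finally, an adjusted sensitivity analysis could sit in a statistical analysis plan that is not at hand. That is true of a supportive analysis. The primary test, however, is fixed in the protocol, and a plan that made another test primary would contradict it.

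**Conclusion.** The point holds as an improvement in efficiency, not as an error. The protocol commits to an unadjusted primary comparison while listing plausible severity covariates as already collected. The planned test is valid and has about 80% power for 50% v 35%.

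Adjustment at the same 334 patients would add about 1 to 2 points of power at an AUC of 0.63 to 0.65, 3 to 4 at 0.69, 5 to 6 at 0.74 and 8 to 9 at 0.78. The cost is at most about 1 point if the covariates are not prognostic.

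These figures rest on assumed prognostic strength, on baseline values being available before the intervention for nearly all patients, and on simulations without centre effects.

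**What to change.** Amend section 11.1.1, with the synopsis and section 11.2 to match, before any comparative data are seen, including at the two-thirds interim:

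- **Primary analysis.** The marginal day-30 risk difference from a logistic model with arm, age, SOFA, log arterial lactate and centre, standardised over all randomised patients, with a robust standard error. This keeps the absolute difference on which the trial is sized; an adjusted odds ratio would be a different, conditional quantity.
- **Covariate timing.** Use the last values before the study intervention.
- **Centre.** Include it as the stratification factor, with small centres pooled or handled by a prespecified rule. With the 17 centres of section 5.1 there are about 20 patients per centre at the end (334/17) and about 13 at the interim (223/17).
- **Missing baseline values.** A simple imputation rule that ignores arm.
- **Interim and final.** Use the same test at both looks.
- **Supportive.** Keep the chi-square, odds ratio and hazard ratio.
- **Other endpoints.** Apply the same model to the mortality and composite endpoints of section 11.1.2 where event numbers allow.

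The cost is a protocol amendment and modest programming. No patients are added and no new variables are needed. Sites should confirm that SOFA and lactate are recorded before the intervention starts.

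### Randomisation is stratified by centre but the primary chi-square is not: alpha is safe and planned power is met, but some power is forgone if centres differ in mortality

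*Protocol*

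**What the plan says.** Protocol section 4.3.1: "Randomization will be stratified on the center". Section 11.1.1 states that the difference between the groups "in the risk of all-cause mortality at day 30 following randomization will be studied using the Chi-2 test". It names no strata and no covariates, and continues: "To illustrate the association, both an odd-ratio and a hazard ratio will be provided". Kaplan-Meier curves are added. Section 11.1.2 applies the same strategy to mortality at 48 hours and days 7, 60 and 180, and to the composite endpoint at days 30, 60 and 180.

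Section 11.2 sizes the trial "considering a total event risk (for the primary endpoint) of 50 % in the control group" to detect a "15% absolute difference in favor the VA-ECMO group using a chi-square test", giving 167 per group at 80% power. Section 1.4.1 also argues clinical relevance from the absolute risk difference. Section 11.3 sets the final threshold at a two-sided p below 4.9%.

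**The concern.** When allocation is balanced within centre, part of the outcome variation (the differences between centres) can no longer move the treatment comparison. A test that ignores centre still counts that variation in its standard error. If centres differ, the p-value is then larger than the design warrants, and a true effect is a little more likely to be missed. Because section 11.1.2 repeats the strategy, the mismatch reaches every mortality and composite analysis.

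A smaller, related point is that the trial is sized and justified on an absolute difference, while the effect measures named in section 11.1.1 are both relative.

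**Working it through.** **1. Reproduce the sample size.** Inputs from section 11.2: 50% v 35%, 80% power, two-sided 5%, two equal groups.

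n = (z₀.₉₇₅ + z₀.₈₀)² × [p₀(1−p₀) + p₁(1−p₁)] / (p₀−p₁)²
= (1.960 + 0.842)² × (0.2500 + 0.2275) / 0.0225 = 166.6, rounded up to 167.

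The pooled-variance version gives 170, and a continuity correction gives 183. The stated 167 is therefore the plain two-proportion figure, with no credit for stratification. At 167 per group and the 4.9% threshold, power is 79.2% (pooled) or 79.9% (unpooled).

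**2. Mechanism.** With p_k the mortality in centre k and p̄ the overall mortality,

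p̄(1−p̄) = average of p_k(1−p_k) + between-centre variance of p_k.

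Balanced allocation within centre largely removes the second term from the true sampling variance of the difference. The chi-square keeps it, and a centre-stratified Cochran-Mantel-Haenszel (CMH) test does not. If the second term is near zero, the two tests agree.

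**3. Size, by simulation.** From the protocol: N = 334; 17 centres (section 5.1) or 20 (synopsis); threshold 4.9%; marginal rates 50% v 35% for power and 50% v 50% for type I error. Assumed, because the protocol gives no figure: blocks of 4 within centre, uneven centre sizes, and normal centre effects on the log-odds with SD 0 to 1.0. There were 40,000 trials per setting, so the Monte Carlo standard error is √(0.8×0.2/40,000) = 0.2 points for power and √(0.049×0.951/40,000) = 0.11 points for type I error. Only the final analysis is modelled.

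| Centres | SD | 95% of centres, mortality | Type I error, chi-square / CMH | Power, chi-square / CMH | Power change |
|---|---|---|---|---|---|
| 17 | 0 | 50% | 4.96% / 4.75% | 79.1% / 78.8% | −0.3 |
| 17 | 0.25 | 38–62% | 4.71% / 4.66% | 79.4% / 79.3% | −0.1 |
| 17 | 0.5 | 27–73% | 4.67% / 4.95% | 80.1% / 81.0% | +0.9 |
| 17 | 0.75 | 19–81% | 4.08% / 5.08% | 81.0% / 83.4% | +2.4 |
| 17 | 1.0 | 12–88% | 3.45% / 4.98% | 81.7% / 85.9% | +4.1 |
| 20 | 0 | 50% | 5.08% / 4.89% | 79.5% / 79.0% | −0.5 |
| 20 | 0.25 | 38–62% | 4.81% / 4.75% | 79.7% / 79.5% | −0.2 |
| 20 | 0.5 | 27–73% | 4.73% / 5.15% | 80.2% / 81.1% | +0.9 |
| 20 | 0.75 | 19–81% | 3.83% / 4.76% | 80.9% / 83.2% | +2.4 |
| 20 | 1.0 | 12–88% | 3.44% / 5.12% | 81.5% / 85.8% | +4.3 |

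A separate 17-centre run gave −0.3, +0.9, +2.3 and +4.5 points at SD 0, 0.5, 0.75 and 1.0, with chi-square type I error of 3.8% and 3.5% at the two largest SDs.

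The chi-square's own power rises slightly with SD because stratified allocation makes the estimate more precise. The test simply does not take full credit for that.

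**4. Effect measures at the design rates.** Odds ratio = (0.35/0.65)/(0.50/0.50) = 0.54; risk ratio = 0.35/0.50 = 0.70; risk difference = −15 points. With mortality near 50%, the odds ratio is far from the risk ratio and does not show the quantity on which the trial was sized.

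**The case against.** The best defence is that analysis and sizing agree. Section 11.2 powers the trial "using a chi-square test with a 80 % power", and that test is the one planned. A reader might infer from the mismatch that the trial throws away power already built into its sample size, or falls short of 80%. The documents do not support this: step 1 shows no stratification credit in N, and the chi-square kept 79% to 82% power in every setting. Nor is there a false-positive risk, because the plain test stays at or below its nominal level apart from simulation noise. With little centre variation, CMH over 17 to 20 strata averaging 334/20 = 17 to 334/17 = 20 patients is equal or very slightly worse. All of this stands.

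A reader might also infer a larger loss from not adjusting for severity, since section 4.1.4 collects "demographic data, medical history, SOFA score, biological data (Arterial Lactate" and more. Gains of about 3.5 to 7 points can be simulated if a baseline score is assumed to have an AUC of 0.70 to 0.76. The protocol gives no prognostic strength, these variables are not stratification factors, and a supportive adjusted model would leave the primary test unchanged. That gain is no part of this point.

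On effect measures, section 11.1.1 calls the two ratios illustrative, does not exclude others, and plans Kaplan-Meier curves that show absolute risk. The absence of a risk difference is therefore not an error, though one is worth naming.

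The objection does not remove the mismatch itself. The protocol fixes the stratification factor and fixes an unstratified test, so the choice has not simply been left to an analysis plan.

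**Conclusion.** The point holds as a matter of alignment and efficiency, not of validity. Type I error is not inflated and planned power is met. The plain test is conservative only to the extent that centre mortality differs. The power forgone is about none at a log-odds SD up to 0.25, about 1 point at 0.5, 2 to 2.5 at 0.75 and 4 to 4.5 at 1.0. Clear conservatism appears only at the two largest values: about 4% at SD 0.75 and 3.5% at SD 1.0, against 4.9%.

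The mismatch is certain from the text. Its size is not, because it rests on an assumed between-centre SD and block size. Some variation is plausible: section 4.1.1 leaves ECMO initiation, therapy and weaning to local practice, and Appendix B lists different devices by site. Neither gives a magnitude. The 17 v 20 centre discrepancy does not alter the result.

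**What to change.** In section 11.1.1, the matching synopsis text and the analysis plan:

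- Make the primary test a Cochran-Mantel-Haenszel test stratified by centre, with a rule for pooling small centres fixed before database lock and preferably before the interim analysis.
- Report the centre-stratified risk difference with 95% CI beside the odds ratio and hazard ratio.
- Keep the crude chi-square as a sensitivity analysis.
- Let section 11.1.2 carry the same stratification to the secondary mortality and composite endpoints.

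A supportive model adjusted for inclusion SOFA and lactate is optional.

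The cost is wording, through the amendment route in section 13.3. No new data or patients are needed and N stays at 334. The statistical downside is about 0.3 to 0.5 power points if centres do not differ.
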